## 5. Data Sources and Data Collection

Data will be extracted from electronic medical records (EMR), including:

1. Demographics (age, sex)
2. *H. pylori* testing method and results (C13 breath test, histology, culture, external hospital data)
3. DOB values for C13 testing
4. Comorbidities
5. Allergy history
6. Concomitant medications
7. Number of eradication attempts
8. Treatment regimen details (drug names, doses, duration, regimen abbreviation)
9. Post-treatment test results

No additional visits, tests, or procedures will be performed.

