## 1. Background and Rationale

*Helicobacter pylori* (H. pylori) infection is highly prevalent in China and is associated with chronic gastritis, peptic ulcer disease, gastric mucosa-associated lymphoid tissue lymphoma, and gastric cancer. Increasing antibiotic resistance has reduced eradication success rates in real-world clinical practice.

Shenzhen Hospital of Southern Medical University manages more than 5,000 H. pylori tests and over 2,000 eradication treatments annually. Despite standardized training, eradication success rates remain suboptimal (<80% in internal data).

This study aims to evaluate the real-world effectiveness of commonly used eradication regimens and identify factors associated with treatment outcomes.

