## 3. Study Design

This is a **single-center, retrospective, observational study** using routinely collected clinical data from Shenzhen Hospital of Southern Medical University.

- **Study Period:** 2016–2023
- **Study Type:** Observational
- **Time Perspective:** Retrospective
- **Sampling Method:** Non-probability, consecutive sampling
- **Intervention:** None (standard-of-care only)

No study-driven treatment or randomization will occur. All treatments are determined by treating physicians as part of routine care.

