### 4.2 Inclusion Criteria

- Age  $\geq$  14 years
- Underwent *H. pylori* testing and/or eradication treatment during the study period
- Diagnosis of *H. pylori* infection based on national consensus guidelines or clinically accepted methods

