## 6. Outcome Measures

### 6.1 Primary Outcome

***H. pylori* eradication success rate**, defined as a negative post-treatment test (C13 breath test, stool antigen, histology, or other accepted method) within 4–12 weeks after therapy.

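### The extraction list names no treatment or test dates although the 4–12 week primary outcome needs them, and calendar year is neither a listed field nor a planned covariate in a comparison pooling 2016–2023

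*Combined protocol and SAP*

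**What the plan says.** Section 6.1 counts a patient as a success on a negative post-treatment test "within 4–12 weeks after therapy".

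Section 5 introduces its nine items with "Data will be extracted from electronic medical records (EMR), including". The treatment item is "Treatment regimen details (drug names, doses, duration, regimen abbreviation"), and the follow-up item is "Post-treatment test results". Another item, "DOB values for C13 testing", is a breath-test measurement and not a date. None of the nine items is a date, and no other section names a prescription, end-of-therapy or test date.

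On calendar time, Section 1 states: "Increasing antibiotic resistance has reduced eradication success rates in real-world clinical practice". Section 3 gives "Study Period: 2016–2023" and leaves the choice of treatment to the physician. The secondary objectives in Section 2.2 are to compare regimens and to look for demographic, clinical and treatment-related factors. Section 9.2 plans chi-square tests and a multivariable logistic regression, and names no covariates.

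**The concern.** Two gaps share one source.

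First, the primary outcome is defined by an interval, and the listed fields do not contain its two endpoints. Treatment duration says how long a course lasted, not when it ended. From the listed items alone, no test can be placed inside or outside the window. For a patient with more than one course, or with a test from another hospital (which Section 5 allows), a result cannot be reliably tied to the right course.

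Second, the plan itself names a time-related influence on the outcome, pools eight years, and compares regimens that were not randomised. If the mix of regimens changed while success was falling, a regimen used mostly in earlier years would look better than an equally effective one used mostly in later years. Nothing in the plan commits the analysis to separating the two. The regimen comparison is at stake here more than the overall success rate.

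**Working it through.** **Step 1: fields needed against fields listed.**

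| Needed | Listed in Section 5? |
|---|---|
| End of therapy, or start date plus duration | Duration only |
| Date of each test | No; method and result only |
| Calendar year of treatment | No |

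The interval and the year are therefore not computable from the nine named items. Section 9.2 names no covariates, so adding dates to Section 5 would not by itself produce an adjustment for year.

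**Step 2: the plan's own figures.** The study period is 2023 − 2016 + 1 = 8 calendar years. The sample size of about 3,000 in Section 9.1 is a count of all eligible patients with no effect size or power, so there is no formula to reproduce.

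**Step 3: possible size of the calendar effect.** The documents give no trend, no regimen mix by year and no number per regimen. The following are assumptions, chosen only to show scale:
- mean success of 80% (Section 1 says only that internal rates are below 80%);
- two equally effective regimens with 1,500 patients each;
- a linear fall of D points from first to last year;
- regimen A has a share s of its use in the first four years, and regimen B has 1 − s.

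The yearly step is D/7, and the first-half and second-half midpoints are four years apart, so the half-period means differ by 4D/7. The spurious gap is (2s − 1) × 4D/7. For s = 0.75 this is 0.5 × 4D/7 = 2D/7:
- D = 5: 10/7 = 1.4 points
- D = 10: 20/7 = 2.9 points
- D = 15: 30/7 = 4.3 points

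The standard error of the difference is √(2 × 0.8 × 0.2 / 1500) = 0.0146, or 1.46 points. The table gives the gap and, in brackets, the chance of a result significant at two-sided 0.05 in the direction of the gap without adjustment for year. With no gap that chance would be 2.5%.

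| Usage split | D = 5 | D = 10 | D = 15 |
|---|---|---|---|
| 60/40 | 0.6 (6%) | 1.1 (12%) | 1.7 (22%) |
| 75/25 | 1.4 (16%) | 2.9 (50%) | 4.3 (84%) |
| 90/10 | 2.3 (35%) | 4.6 (88%) | 6.9 (>99%) |

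**Step 4: sensitivity to how the fall is defined.** If the 10 points run continuously from 85% at the start of the period to 75% at the end, the half-period means are 82.5% and 77.5%, which differ by 5 points. A 75/25 split then gives 2.5 points, z = 2.5/1.46 = 1.71, P about 0.09. Only complete separation of the regimens by period gives the full 5 points (z = 5/1.46 = 3.4).

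**The case against.** A reader might infer that the primary outcome cannot be derived and that drift cannot be adjusted for. The documents do not support that. The list in Section 5 opens with an inclusive phrase and reads as content categories, not a closed data dictionary. Eligibility rests on patients who "Underwent *H. pylori* testing and/or eradication treatment during the study period", so at least one event date must be read from the records to build the cohort. Counting attempts before success (Section 6.2) also requires courses and tests to be put in order. The dates are unlisted; they are not shown to be unobtainable. Nor does it follow that tests at any time would be counted, because Section 6.1 sets the window. This half can fairly be called loose drafting.

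A reader might also infer that earlier regimens will be favoured, or that a highly significant false difference is to be expected. Neither is established. Section 1 makes a general statement about resistance, with no trend size for this hospital and no regimen use by year. A z of 3.4 needs regimens that never overlap in time.

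Finally, because no covariates are named, the omission of year is one instance of a wider gap, and an open covariate set does not rule year out.

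All of this limits how strongly the point can be put. It does not remove it. A date used for cohort selection is not an end-of-therapy date and a test date for each course, and an open list obliges nobody to extract them. Calendar time does not obviously fall under the demographic, clinical and treatment-related factors of Section 2.2, so an analyst following the plan could omit it without departing from it.

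**Conclusion.** The point holds as a gap in specification that should be closed. The extraction list does not name the dates on which the primary outcome depends. Taken alone, this is close to a missing detail. The calendar-year omission carries more weight: the plan names a time-related cause of lower success, pools eight years of non-randomised regimen choices, and commits to no adjustment for time.

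If regimen use shifted over 2016–2023, the regimen comparisons would be confounded by calendar time. The size is unknown from the documents. Under the stated assumptions the spurious gap is about 1.4 to 4.3 points for a 75/25 split, and from about 0.6 to 6.9 points across all the splits shown. If usage did not shift, or success did not change, there is no such bias. The conclusion rests on the text of Sections 1, 3, 5, 6.1 and 9.2, not on the illustrative figures.

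**What to change.** Before extraction:

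1. In Section 5, make these required fields: start and end date of each eradication course, and date and method of each *H. pylori* test, including tests from other hospitals where the date is available.
2. In Section 6.1 or 9.2, derive weeks from end of therapy to test and use them to apply the 4–12 week window. State how tests outside the window, repeated tests and missing dates are handled.
3. In Section 9.2, name calendar year (or period) of treatment as a covariate in the logistic model that compares regimens.

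A sensitivity analysis that counts any test at or after 4 weeks and before a later course is optional.

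The cost is a few more fields from the same records and one more model term. Where regimen and year overlap little, the adjusted comparison will lose some precision; a table of regimen by year would show where. The timing matters because Section 8 allows no changes after database lock apart from corrections during programming, so an omitted field would be hard to recover.

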## 6. Outcome Measures

### 6.1 Primary Outcome

***H. pylori* eradication success rate**, defined as a negative post-treatment test (C13 breath test, stool antigen, histology, or other accepted method) within 4–12 weeks after therapy.

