### 2.2 Secondary Objectives

- To identify demographic, clinical, and treatment-related factors associated with eradication success or failure.

- To compare the effectiveness of commonly used eradication regimens in routine clinical practice.

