### 4.3 Exclusion Criteria

- Age  $<$  14 years
- Pregnant or breastfeeding women
- Patients deemed unsuitable by the investigator

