#### Multivariate Analysis

- Multivariable logistic regression to identify independent predictors of eradication success

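### The primary outcome accepts a negative test whatever drugs the patient is taking at the time, so a masked infection is recorded as a cure

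*Combined protocol and SAP*

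**What the plan says.** Section 6.1 gives the primary outcome as the eradication success rate, "defined as a negative post-treatment test (C13 breath test, stool antigen, histology, or other accepted method) within 4–12 weeks after therapy". The method may vary and the timing is bounded, but drugs in use on the day of the test are not mentioned.

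No other section supplies the condition:

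- Section 4.2 refers to consensus guidelines for the diagnosis that brings a patient into the study, not for the test that decides the outcome.
- Section 4.3 excludes by age, by pregnancy or breastfeeding, and under "Patients deemed unsuitable by the investigator". None of these is a rule about test conditions.
- Section 5 lists "Concomitant medications" and "Post-treatment test results" as data items, with no drug dates and no link between drug and test. It also states: "No additional visits, tests, or procedures will be performed".
- Section 9 adds no rule on which tests can be assessed.

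The factor objective in 2.2 reads "To identify demographic, clinical, and treatment-related factors associated with eradication success or failure", and section 9.2 plans "Multivariable logistic regression to identify independent predictors of eradication success" without a covariate list.

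**The concern.** Acid suppressants, antibiotics and bismuth can lower bacterial load or urease activity and turn a test negative while the infection persists. This is general diagnostic knowledge and is not stated in the documents. The 4-week minimum deals with the eradication course itself. It does not deal with an acid suppressant continued afterwards or an antibiotic started for another reason. As 6.1 is written, a negative breath test in week 5 on daily acid suppression is a success.

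Two results are exposed. For the primary objective, masking converts failures into successes and never the reverse, so rates rise even when regimens are balanced on drug use. For the factor objective, a drug in use at the test, or a comorbidity that leads to its use, could appear to improve eradication when it only hides failure. The study is retrospective with no retesting, so only the outcome rule can deal with this.

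**Working it through.** **Inputs.** The plan gives no figure for this effect, so there is none to reproduce. From the documents: internal success below 80% (section 1), about 3,000 patients (9.1, a head count with no power or precision target), and two-sided tests at 0.05 (9.2). Assumed: true success p = 78%; f = share of persisting infections tested on a masking drug, 10–30%; s = share of those reading negative, 10–40%; no false positives.

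**1. Overall rate under the current rule.** Inflation = (1 − p) × f × s = 22 × f × s points.

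- f = 10%, s = 10%: 22 × 0.01 = 0.2
- f = 20%, s = 25%: 22 × 0.05 = 1.1
- f = 30%, s = 40%: 22 × 0.12 = 2.6

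With p from 75% to 79% and f from 5% to 30%, the range is 0.1 (21 × 0.05 × 0.10) to 3.0 points (25 × 0.30 × 0.40).

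**2. Spurious odds ratio for a drug with no effect on cure.** Apparent success on drug = 1 − 0.22 × (1 − s). Off drug it is 0.78, with odds 0.78/0.22 = 3.545.

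- s = 10%: 0.802/0.198 = 4.051; ratio 1.14
- s = 30%: 0.846/0.154 = 5.494; ratio 1.55
- s = 40%: 0.868/0.132 = 6.576; ratio 1.85

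This supposes that off-drug tests miss nothing. If they detect only 95% of persisting infections, apparent off-drug success is p + 0.05 × (1 − p). At p = 75% that is 0.7625 (odds 3.211). The ratios become (0.775/0.225)/3.211 = 1.07 at s = 10% and (0.85/0.15)/3.211 = 1.77 at s = 40%. At p = 79% they are 1.07 and 1.73.

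**3. Chance that such an effect reaches significance.** Take an unadjusted comparison of two proportions with 3,000 patients and 95% off-drug sensitivity. Here f is the share of all patients tested on drug, and the chance is Φ((d − 1.96 × SE0)/SE1), with SE0 pooled and SE1 unpooled. Example: p = 75%, f = 10%, s = 40%. Then d = 0.85 − 0.7625 = 0.0875 with 300 against 2,700 patients, SE0 = 0.0256 and SE1 = 0.0222, so the chance is Φ(1.69) = 0.95. Over f = 5–30% and p of 75% and 79%:

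- s = 10%: 5–11%
- s = 20%: 14–62%
- s = 40%: 62–100%

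**4. Which repair works.** Suppose the same share f is exposed among cured and uncured patients, and there is no later test. Dropping only the on-drug negatives, while keeping on-drug positives as failures, gives p(1 − f) / [(1 − f) + (1 − p) × f × (1 − s)]. Dropping every on-drug test gives p(1 − f)/(1 − f) = p.

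| f, s | Current rule | Drop on-drug negatives only | Drop all on-drug tests |
|---|---|---|---|
| 10%, 10% | 78.2% | 0.702/0.9198 = 76.3% | 78.0% |
| 20%, 25% | 79.1% | 0.624/0.833 = 74.9% | 78.0% |
| 30%, 40% | 80.6% | 0.546/0.7396 = 73.8% | 78.0% |

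Dropping only negatives is further from 78% than the current rule in every row. It also leaves every assessable exposed patient a failure, which would reverse the spurious association in a factor model.

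**The case against.** The strongest objection is that the size is unknown and may be small. Neither f nor s has any basis in the documents. At 3,000 patients and 78%, the 95% half-width is 1.96 × √(0.78 × 0.22/3,000) = 1.5 points, so of the three scenarios only the highest exceeds sampling error. This stands as a limit on size. It does not remove the point, because the bias has one direction and does not shrink as patients are added.

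A reader might infer more than the documents support in three ways:

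- *That the plan enters concomitant drugs in the regression.* Section 5 only lists them as collected, and 9.2 names no covariates. The spurious predictor is a likely consequence of the objective in 2.2, not a stated analysis.
- *That many of these patients are on acid suppression at the test.* Section 1 names ulcer and gastritis as diseases associated with the infection; the documents do not describe the cohort's case mix.
- *That the needed dates are already in hand.* Section 5 names the electronic record as the source but lists no drug dates, so the extraction must be specified.

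It could also be said that the reference to accepted methods, or the investigator's discretion over suitability, implies proper test conditions. Neither is an explicit rule that a second analyst could apply the same way.

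**Conclusion.** The point holds: 6.1 does not separate cure from suppression by a drug in use at the test, nothing else in the plan does so, and the resulting error runs only toward success. With 78% true success and the assumed exposure and masking ranges, the overall rate is overstated by about 0.2 to 2.6 points. The factor analysis is more exposed: if these drugs are examined, a drug with no effect could show an odds ratio of about 1.14 to 1.85, or about 1.07 to 1.77 with 95% off-drug sensitivity. These are illustrations under assumptions. They do not show that this cohort's rates are materially wrong. The change is worth making before analysis because it is modest and cannot be replaced by later testing.

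**What to change.** 1. In section 5, add the dates of acid suppressants, antibiotics and bismuth, and the date of the post-treatment test, so that exposure at the test can be derived.
2. In section 6.1, define an assessable test by drug exposure and not by its result. Make the main rate the one among tests taken outside the washout window of the consensus guideline the site uses, and cite that guideline. Exclude both negatives and positives taken inside the window.
3. Where a later unexposed test exists within the 12 weeks, use it whatever the first result was. Report how many patients enter this way, since retesting may itself depend on the first result.
4. Report the all-tests rate under the current rule as a sensitivity analysis, with the number of tests excluded by regimen.
5. In the factor analysis, separate medication taken during the eradication course from medication taken at the time of the test.

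The costs are the extraction of drug dates, a smaller assessable set, and over-the-counter use that the record will not show. The main rate then describes patients tested off drug; it equals the rate for all tested patients only if exposure at the test is unrelated to true cure.

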### 6.2 Secondary Outcomes

- Factors associated with eradication success or failure
- Comparison of eradication rates across regimens
- Distribution of comorbidities
- Number of eradication attempts before success

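### The regimen comparison does not commit to adjusting for calendar year, and the attempt count it could adjust for can be read as a total that failure raises

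*Combined protocol and SAP*

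**What the plan says.** Section 2.2 has two separate secondary objectives: "To identify demographic, clinical, and treatment-related factors associated with eradication success or failure" and "To compare the effectiveness of commonly used eradication regimens in routine clinical practice". Section 6.2 repeats the second as "Comparison of eradication rates across regimens". Section 3 describes a retrospective study over 2016–2023 without randomisation, in which "All treatments are determined by treating physicians as part of routine care".

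Section 9.2 gives t-tests and chi-square tests under univariate analysis, then a multivariable logistic regression whose stated purpose is to find predictors of success. It names no regimen contrast, reference regimen or covariates.

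Section 5 opens its list with "Data will be extracted from electronic medical records (EMR), including" and includes regimen details, "Number of eradication attempts", allergy history, comorbidities and concomitant medications. Neither a treatment date nor calendar year is named. Section 6.2 separately lists how many attempts preceded success. Neither attempt item is defined.

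Section 1 states "Increasing antibiotic resistance has reduced eradication success rates in real-world clinical practice", and reports that locally "eradication success rates remain suboptimal (<80% in internal data").

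**The concern.** When physicians choose the regimen, groups may differ in ways that also affect success. Two such factors stand out here.

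- **Calendar time.** The plan itself says success has fallen as resistance rose. A regimen used mostly in later years would then look worse than one used mostly in earlier years, even if the two were equally effective.
- **Earlier failure.** If retreatment succeeds less often, a regimen given more often as retreatment looks worse in a crude comparison. The natural remedy is to adjust for the attempt count. That works if the count covers courses before the analysed one. If it is a total that includes later courses, failure of the analysed course raises it, so the model conditions on a consequence of the outcome.

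A crude chi-square ranking and a model using a total count are both compatible with the text. At stake is the ranking of regimens, which clinicians are likely to use.

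**Working it through.** The plan has no figure to reproduce for this point. The estimate of about 3,000 patients comes without an effect size, power or split by regimen. The size of the problem can only be illustrated.

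**Inputs.** From the documents: two-sided testing at 0.05 (9.2), eight calendar years (3), overall success below 80% (1). Assumed: success by line of treatment, retreatment shares, usage trends, and 300 or 500 patients per regimen. The true regimen effect is set to zero throughout.

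**Step 1: attempt mix, crude rates.** Rate = (1 − s) × first-line success + s × retreatment success, where s is the retreatment share.
- Mild (80% and 70%; s = 10% in A, 20% in B): A = 0.9×0.80 + 0.1×0.70 = 0.790; B = 0.8×0.80 + 0.2×0.70 = 0.780.
- Moderate (80% and 65%; s = 10% in A, 30% in B): A = 0.9×0.80 + 0.1×0.65 = 0.785; B = 0.7×0.80 + 0.3×0.65 = 0.755.

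**Step 2: calendar drift, crude rates.** Yearly success falls linearly. Usage falls linearly over the eight years for A and is mirrored for B. With 3:1 usage, the mean year index (0 to 7) is 2.75 for A and 4.25 for B. A fall from 80% to 75% then gives 0.80 − 0.05×2.75/7 = 0.7804 and 0.80 − 0.05×4.25/7 = 0.7696. The other cases follow in the same way.

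**Step 3: chance of a false finding.** This is the two-proportion normal approximation, for a single pair of regimens. Example, moderate at 500: the null standard error is √(2×0.77×0.23/500) = 0.0266, and (0.03 − 1.96×0.0266)/0.0266 = −0.83, giving about 20%.

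| Assumed scenario | A vs B | Gap (points) | Rejection at 300 / 500 |
|---|---|---|---|
| Attempt mix, mild | 79.0% vs 78.0% | 1.0 | 6% / 7% |
| Attempt mix, moderate | 78.5% vs 75.5% | 3.0 | 14% / 20% |
| 80% to 75%, 3:1 | 78.0% vs 77.0% | 1.1 | 6% / 7% |
| 80% to 75%, 8:1 | 78.3% vs 76.7% | 1.7 | 8% / 10% |
| 82% to 72%, 3:1 | 78.1% vs 75.9% | 2.1 | 10% / 13% |
| 82% to 72%, 8:1 | 78.7% vs 75.3% | 3.3 | 16% / 24% |

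In simulation (4,000 runs per cell), adjusting for prior attempts gave rejection of 4.3–6.0%, and adjusting for year 4.5–6.0%.

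**Step 4: adjusting for a total count.** Let total = prior + 1, plus 1 more if the analysed course failed and another recorded course followed (probability q after failure). Take the moderate case with q = 0.3 and one earlier course per retreatment patient, and look at patients with a total of 2:
- A: successes 0.1×0.65 = 0.065; failures 0.1×0.35×0.7 + 0.9×0.20×0.3 = 0.0785; success 0.065/0.1435 = 45%.
- B: successes 0.3×0.65 = 0.195; failures 0.3×0.35×0.7 + 0.7×0.20×0.3 = 0.1155; success 0.195/0.3105 = 63%.

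The regimens are equally effective, yet B, which has more retreatment, now looks better. With the total entered linearly in the logistic model, the false odds ratio for B versus A is:

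| q | Moderate: odds ratio; rejection at 300 / 500 | Mild: odds ratio; rejection at 300 / 500 |
|---|---|---|
| 0 | 1.00; no bias | 1.00; no bias |
| 0.1 | 1.10; 8% / 10% | 1.06; 6% / 7% |
| 0.3 | 1.30; 22% / 34% | 1.18; 12% / 17% |
| 0.5 | 1.56; 47% / 68% | 1.30; 20% / 30% |

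The crude bias from attempt mix in Step 1 disfavours B. The total-count bias favours B.

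**The case against.** The strongest reply is that an adjusted comparison is the natural reading. Treatment-related factors are among the predictors sought, regimen and attempts are collected, and a model in a study of regimens that left out regimen would be odd. Chi-square already sits under univariate analysis. This largely stands: the unnamed covariates and reference regimen are missing detail, not a missing method. It does not cover calendar year, which the listed items leave uncontrolled, or the definition of the attempt count.

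A reader might infer that dates will not be available. The documents do not support that: the Section 5 list is open, and the 4–12 week test window in 6.1 cannot be applied without dates. Only the commitment to use them is missing.

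A reader might also infer that adjusting for attempts is bound to mislead. It is not. If the last course is analysed, the total equals prior attempts plus one and there is no bias. If each course is a row, the count would naturally be its order. The harm needs a later counted course after the analysed one, which is one of several possible readings.

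Finally, every scenario input is assumed. At 300–500 per regimen, about 3,000 patients would mean 6–10 regimens, and a global test across them would behave differently from these pairwise figures.

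**Conclusion.** The point holds as a worthwhile, inexpensive improvement to a secondary aim. Under the assumed scenarios, a crude comparison of equally effective regimens shows gaps of about 1.0–3.3 points and is significant in 6–16% of cases at 300 per regimen and 7–24% at 500, against a nominal 5%. A total attempt count that includes later courses would give a false odds ratio of about 1.06–1.56 favouring the regimen with more retreatment. Because this runs opposite to the crude attempt-mix bias, the two errors should not be added together.

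It would go too far to say that the regimen comparison is shown to be confounded. The documents do not say what drove regimen choice, how use changed over the years or what share was retreatment, so the actual bias is unknown and may be small. The primary objective, describing success by regimen, is unaffected. Confidence is high on the omission and much lower on its consequence.

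**What to change.** In Section 5:
- Name the treatment start date as a data item.
- Define the attempt number as courses before the analysed course, and state whether courses at other hospitals count.
- State the unit of analysis: one defined course per patient, or all courses with patient-clustered standard errors.

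In Section 9.2:
- Base the regimen comparison on the logistic model with regimen as the exposure and a named reference. Adjust for prior attempts and calendar year in addition to the baseline items already collected (age, sex, allergy history, and comorbidities and concomitant medications recorded before treatment).
- Treat the chi-square result as crude.
- Tabulate regimen use by year first. Where regimens barely overlap, report that the comparison is not supported.

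Adjusted risk differences and a first-attempt-only sensitivity analysis are optional.

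The cost is SAP wording and dates already in the records. In the assumed scenarios the standard error of the regimen log odds ratio rises about 2–5% for prior attempts (0.154 to 0.157 mild, 0.151 to 0.159 moderate, at 500 per regimen). For year it rises about 7–18% (0.151 to 0.161 with 3:1 usage at 500 per regimen; 0.195 to 0.230 with 8:1 at 300). If 90–95% of each regimen's use fell in opposite halves of the period, adjusting for year would multiply it by about 1.7–2.3, which is the reason for the overlap check. Residual confounding by unrecorded reasons for regimen choice would remain.
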